## 7.1.3 Methods for Handling Missing Data

Missing pain and daily activities data for participants in the mITT population will be imputed via last observation carried forward (LOCF). Prior to imputing missing endpoint data for the endpoint sustained pain relief 15-60 minutes, pain relief will be assessed at each of the 15, 20, 30, and 60-minute timepoints that have data available. If any of these

Protocol: CP-2019-001 Page 15 of 26

Final Version 1.0

timepoints has a pain severity rating of moderate or severe, or if the subject has used a rescue medication/therapy, then the subject will be considered to have not achieved sustained pain relief and this endpoint will not be imputed. Otherwise, missing pain data will be imputed using LOCF. Missing data for all sustained pain relief and sustained pain freedom endpoints will be handled this way.

Missing safety data will not be imputed. Due to COVID-19, it is unavoidable that some subjects will be missing certain safety assessments, such as (but not limited to) Visit 3 clinical labs, vital signs, and ECG. This is because the Visit 3 occurred during the pandemic and telemedicine visit was necessary. Safety summaries will be generated using observed data, and missing safety assessments will be captured as protocol deviations.

Missing rescue medication data will be handled as described in section 7.2.4.4.

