#### 7.2.3 Sustained Pain Relief

The other co-primary efficacy endpoint is the proportion of subjects who achieve sustained pain relief from 15 minutes to 60 minutes post patch administration. Sustained pain relief requires a pain rating of mild or none at each timepoint from 15 minutes to 60 minutes without the use of acute rescue medication at any time during the 60 minutes post patch administration.

Protocol: CP-2019-001 Page 16 of 26

Final Version 1.0

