## 9.1.1 Sensitivity and Supporting Analyses

The primary analysis may be followed by a sensitivity analysis to investigate the impact of missing data on the treatment estimates.

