#### 9.1.1.1 C213 patients as failure and placebo as responder

If performed, this sensitivity analysis will be a repeat of the primary efficacy analysis where C213 patients with missing data will be imputed as non-responders/failures, and placebo patients with missing data as responders. Thus, for the co-primary outcome measure of pain relief at 15 minutes, C213 patients with a missing pain score at 15 minutes will be considered a treatment failure, and placebo patients with missing data at 15 minutes will be considered a responder. For the co-primary outcome measure of sustained pain relief, C213 patients with a missing pain score at any time from 15-60 minutes will be considered a treatment failure, and placebo patients with a missing pain score will be considered a responder only if all other pain scores within 15-60 minutes are not severe or are missing.

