### 12. CHANGES FROM PLANNED ANALYSIS

Due to insufficient enrollment numbers, the CMH test as described in the protocol for the primary and secondary analyses will not be performed. The protocol also describes a fixed sequential procedure to control for overall type 1 error. This will not be implemented since the actual number of randomized subjects is quite a bit less than planned and the pre-specified statistical analyses as described in the protocol cannot be performed.

Protocol: CP-2019-001 Page 25 of 26

Final Version 1.0

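### The worst-case rule for sustained relief lets a placebo subject with a recorded moderate score count as a responder, although SAP 7.1.3 makes that subject a definite failure

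*SAP*

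**What the plan says.** Three parts of the SAP bear on this.

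- **Endpoint (7.2.3).** "Sustained pain relief requires a pain rating of mild or none at each timepoint from 15 minutes to 60 minutes", with no rescue medication in the 60 minutes.
- **Missing data, primary analysis (7.1.3).** Before any imputation, the recorded scores at 15, 20, 30 and 60 minutes are examined. The screen is met when one of those "timepoints has a pain severity rating of moderate or severe, or if the subject has used a rescue medication/therapy". The section gives the consequence directly: "then the subject will be considered to have not achieved sustained pain relief and this endpoint will not be imputed". Only the remaining subjects have gaps filled by LOCF.
- **Worst-case sensitivity analysis (9.1.1.1).** C213 subjects with any missing score from 15 to 60 minutes are failures. In the other arm, "placebo patients with a missing pain score will be considered a responder only if all other pain scores within 15-60 minutes are not severe"; further missing scores do not count against the subject.

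The analysis is optional. Section 9.1.1 says the primary analysis "may be followed by a sensitivity analysis to investigate the impact of missing data on the treatment estimates", and 9.1.1.1 begins "If performed, this sensitivity analysis will be a repeat of the primary efficacy analysis".

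**The concern.** The scale is 0 none, 1 mild, 2 moderate, 3 severe. A condition of not severe therefore accepts a score of 2, which the endpoint definition and the primary missing-data rule both treat as failure.

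A worst-case analysis should ask how bad the result could be over all the values that the missing scores might take. It should not change outcomes that the recorded scores have already settled. This rule does so, and only in the placebo arm. A placebo subject with a moderate score and complete data is a failure. The same subject with one missed diary entry becomes a success.

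At stake is the meaning of the robustness check on a co-primary endpoint. The placebo rate can be pushed above anything the missing data allow, so a sustained-relief result that survives a proper worst case could be reported as fragile.

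**Working it through.** **1. Two example subjects.** Both are on placebo, with no rescue use and the 60-minute score missing.

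| Scores at 15 / 20 / 30 / 60 min | SAP 7.1.3 | SAP 9.1.1.1 |
|---|---|---|
| moderate / moderate / moderate / missing | failure, not imputed | responder |
| mild / moderate / mild / missing | failure, not imputed | responder |

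No value at 60 minutes could make either subject a success under 7.2.3.

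**2. How many score patterns conflict.** There are four timepoints, each with one of five states (0, 1, 2, 3, missing) and no rescue use.

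- Patterns with at least one missing score: 5⁴ − 4⁴ = 625 − 256 = 369.
- Accepted as placebo responders under 9.1.1.1 (each score 0, 1, 2 or missing, at least one missing): 4⁴ − 3⁴ = 256 − 81 = 175.
- Accepted if the condition were mild or none: 3⁴ − 2⁴ = 81 − 16 = 65.
- Patterns that 9.1.1.1 accepts and 7.1.3 fails: 175 − 65 = 110.

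These are counts of possible patterns, not expected frequencies. With a mild-or-none condition the conflict is zero.

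**3. Planning figures.** SAP section 5 assumes 20% against 55%, 40 per arm, 15% dropout and about 80% power. Evaluable n is 40 × 0.85 = 34 per arm. The continuity-corrected chi-square power at 34 per arm is 79.6%, so the stated power reproduces.

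**4. Size of the effect.** Each wrongly recoded placebo subject adds 1/n to the placebo rate: 1/34 = 2.9 points, 1/20 = 5.0, 1/15 = 6.7, 1/10 = 10.

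The p-values below are two-sided Fisher's exact, the test named in SAP 9.1. Responder counts are close to the planned rates. The evaluable n and the number recoded are assumptions, because the documents give neither.

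| n per arm | C213 responders | Placebo responders | p |
|---|---|---|---|
| 34 | 19 | 7 (none recoded) | 0.0055 |
| 34 | 19 | 8 | 0.0125 |
| 34 | 19 | 9 | 0.026 |
| 34 | 19 | 10 | 0.049 |
| 34 | 19 | 11 (four recoded) | 0.087 |
| 20 | 11 | 4 (none recoded) | 0.048 |
| 20 | 11 | 5 (one recoded) | 0.105 |
| 15 | 8 | 3 (none recoded) | 0.128 |
| 10 | 6 | 2 (none recoded) | 0.170 |

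**5. Starting from a correct worst case.** Suppose legitimate imputation at 34 per arm moves one C213 responder to failure and one placebo subject with no recorded failure to responder. That gives 18 against 8, p = 0.024. The rule as written, with one or two further moderate-score subjects recoded, gives 18 against 9 (p = 0.0465) or 18 against 10 (p = 0.084).

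**The case against.** **The 7.1.3 screen may carry over.** The analysis is described as a repeat of the primary one, and the placebo condition, read strictly, is necessary rather than sufficient. An observed moderate score might then still mean failure. This reading does not survive, because a carried-over screen would already remove severe scores and leave the not-severe clause with nothing to do. The clause sets its own, looser threshold, and the section gives no other placebo criterion for this endpoint. Rescue use is different: 9.1.1.1 is silent on it, so the no-rescue condition is probably inherited, though it should be stated.

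**The analysis is optional and deliberately conservative.** This is true. The error cannot produce a false efficacy claim, feeds no decision rule, and leaves the primary result and the 15-minute worst-case rule unchanged. That limits the seriousness but does not make the classification right.

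**The harm is not shown at realistic sizes.** Much of this stands. At 34 per arm, with C213 held fixed, significance is lost only at the fourth recoding, which is 4/34 = 12% of the placebo arm. SAP 12 says "the actual number of randomized subjects is quite a bit less than planned", so the smaller sizes may be closer to the truth. At 20 per arm, 11 against 4 is already on the edge: one legitimate change in the C213 arm gives 10 against 4, p = 0.096. At 15 or 10 per arm no significance is there to lose, and only the estimate is distorted.

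**Few subjects may be affected.** They must be on placebo and in the mITT population, with a missing score and a moderate but no severe score from 15 to 60 minutes. SAP 3.4 lists alarms and reminders to limit missing entries. The count may be zero.

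**Conclusion.** The rule is wrong as written. Followed literally, it turns a recorded failure into a success, in the placebo arm only, whenever another score is missing. It contradicts SAP 7.1.3 and 7.2.3 and goes beyond the worst case that the missing data allow.

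The bias is against C213, at 1/n per affected placebo subject. Whether it would change a reading of significance depends on the evaluable n and the number affected, both unknown. In the illustrations it takes four recodings at 34 per arm with C213 held fixed, two after a modest legitimate worst case (18 against 8), and one at 20 per arm, where the starting result is already borderline. The correction should be made because the conflict is plain and the edit costs almost nothing, but it is not a threat to the primary conclusion.

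**What to change.** In SAP 9.1.1.1, replace the placebo condition for sustained relief with wording such as:

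> A placebo subject with one or more missing scores at 15, 20, 30 or 60 minutes is counted as a responder only if every recorded score at those times is mild or none and there is no rescue use in the 60 minutes (Section 7.2.4.4). A subject who is a failure on recorded data under Section 7.1.3 remains a failure in every arm.

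The last sentence changes no classification once the first is in place. It states the principle so that it cannot be programmed in two ways.

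The cost is one edit to the SAP before database lock, with no change to data collection or conduct. If the database is already locked, record the intended rule as a dated clarification before this analysis is reported.

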#### 9.2 Secondary Efficacy Analyses

Binary data, with the exception of rescue therapy use, will be summarized by treatment group. Missing data will be imputed using LOCF. Summaries of the proportion of subjects will be calculated and displayed, and a Fisher's Exact test will be performed. Two-sided p-values for the test of no difference between each C213 treatment group and placebo will be provided. Rescue therapy use as reported on the eDiary will be listed by subject and timepoint.

Protocol: CP-2019-001 Page 20 of 26

Final Version 1.0

These endpoints will include:

• Proportion of subjects that achieve pain relief at 5, 10, 20, and 30 minutes post patch application

- Proportion of subjects that achieve sustained pain relief from 5 to 60 minutes and from 10 to 60 minutes post patch application
- Proportion of subjects that achieve pain freedom at 10 minutes and 15 minutes post patch application
- Proportion of subjects that achieve sustained pain freedom from 10 to 60 minutes and from 15 to 60 minutes post patch application
- Proportion of subjects using rescue therapy within 20 minutes post patch application
- Proportion of subjects able to perform their usual daily activities as assessed by the subject at 5, 10, 15, 20, 30, and 60 minutes post patch application

## 9.3 Exploratory Efficacy Analyses

Depending on sample size, the primary efficacy analyses were to be conducted for the subgroup of patients in the mITT population who were in the trial prior to Protocol Amendment 3 and for those who were enrolled after Amendment 3, with the purpose of assessing the impact of the modification of time zero to be the start of the first patch application.

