6 STUDY PROCEDURES AND SCHEDULE

6.1 Study Schedule

A schedule of study procedures is presented in Table 4.

Table 4: Schedule of Study Procedures

	VISIT 1 ¹ Screening [+3 days]	VISIT 2 Randomization Day ¹	48 Week Double-blind Period [+ or – 7 days]	VISIT 3 End of Study (or Early Discontinuation) [+ 3 days]
Procedure	Up to 1 week prior to Randomization	Day 1 – start of double-blind period	Day 1 – Day 336	Day 1-8
Informed Consent	X			
Inclusion/Exclusion Criteria	X	X		
Medical History including Cluster headache, nicotine, alcohol use, and substance abuse history	X			
Demographics	X			
Randomization		X		
Physical Exam	X	X		X
Weight ² /Height	X	X^2		X ²
Vital Signs	X	X		X
Adverse Events Collection		X		X
Concomitant meds/therapies Collection	X	X		X
Chemistry, coagulation & Hematology (fasting) ³	X ³			X
Serum or Urine Pregnancy 4 (only for WOCBP)	X - Serum	X – Urine dipstick	X – Urine dipstick ⁴	X - Serum
Drug Abuse Testing	X			
12-lead ECG	X			X
Train on patch application using demonstration patches		Х		
Train/dispense eDiary		X		
Dispense CTM		X		
Study Drug Self- Administration			X	
Subject eDiary Assessments			X	
Investigator Skin Assessment		X		X
Investigator Phone call to subject ^{5, 6}			X ^{5, 6}	
Collect Unused Patch(es) and Applicator/Perform Drug Accountability				X
Collect eDiary				X

- Qualifying headache and treatment of a cluster headache must occur within 48 weeks of randomization
- Both height and weight at screening only and weight only at visit 2 and 3
- Clinically significant abnormal lab values may be repeated and if not clinically significant on repeat, subject may be eligible for randomization
- ⁴ Urine pregnancy for WOCBP will be collected monthly [+ or 7 days] after randomization day 1 to ensure no pregnancy prior to study drug administration.
- Following randomization, the investigator (or designee) will contact the subject monthly [+ or 3 days] to assess for adverse events, concomitant medications and to provide study related reminders regarding eDiary use and/or C213 application instructions in advance of the qualifying cluster attack.
- The investigator (or designee) will contact the subject within 2 days after C213 application to assess for Adverse Events and to schedule the subject for a final visit 1-8 days after C213 application.

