6.1.2 Visit 2, Day 1 Randomization

- Perform physical exam, including weight
- Perform investigator skin assessment of the upper arm where patches are intended to be applied
- Record vital signs: temperature, respiratory rate (RR), blood pressure (BP), and heart rate (HR)
- Record concomitant medications, including medication taken to treat cluster headaches
- Urine pregnancy for all WOCBP
- Record Adverse events
- Train the subject on how to apply the patches to the upper arm with the demo applicator and have the subject practice applying the demo patches to his/her arm 2-3 times (more is allowable, if necessary)
- Review the definition of a qualifying cluster headache for the study with the subjects
- Record that the subject can apply patches with the applicator unaided
- Reconfirm subject's eligibility based on inclusion/exclusion criteria
- Randomize subject
- Dispense CTM kit that includes the applicator and one dose (each dose consists of 2 patches) as assigned by the RTSM in Medidata

- Provide instructions for scheduling the next visit within 1-8 days of experiencing and treating a qualifying cluster headache with C213
- Remind the subject that if rescue therapy is required, rescue therapy other than a triptan or ergot is permitted at or after 20 minutes post study drug administration.
- Provide eDiary training necessary and dispense the eDiary

6.1.3 Double-Blind Treatment Phase: Day 1 through up to 48 Weeks [336 Days + or – 7 days]

Subjects will have up to 48 weeks to confirm and treat a qualifying cluster headache. Subjects will be instructed to complete the eDiary at the time of a suspected cluster headache. Once the eDiary confirms that the subject has a "qualifying" cluster headache, the subject will follow the steps provided to self-administer the study drug.

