#### 1. OVERVIEW

This Statistical Analysis Plan (SAP) describes the planned analysis and reporting for protocol CP-2019-001: A randomized, double-blind, multi-center, parallel-group comparison of the efficacy and safety of the C213 (Zolmitriptan Microneedle System) to placebo for the acute treatment of cluster headaches, dated 27 June 2019, Amendment 1, dated 16 July 2019, Amendment 2, dated 01 October 2019 and Amendment 3, dated 15 April 2020.

The structure and content of this SAP provides sufficient detail to meet the requirements identified by FDA, European Medicines Agency (EMA), and International Council for Harmonization (ICH) of Technical Requirements for Registration of Pharmaceuticals for Human Use: Guidance on Statistical Principles in Clinical Trials.

The planned analyses identified in this SAP may be included in clinical study reports (CSRs), regulatory submissions, or future manuscripts. Also, post-hoc exploratory analyses not necessarily identified in this SAP may be performed to further examine study data. Any post-hoc, or unplanned exploratory analysis performed will be clearly identified as such in the final CSR.

In preparation of this SAP, the following documents were reviewed and considered in addition to the literature references cited in this SAP:

- Clinical Research Protocol CP-2019-001 Final v1.0 issued 27 June 2019, Amendment 1, dated 16 July 2019, Amendment 2, dated 01 October 2019 and Amendment 3, dated 15 April 2020.
- Case report forms (CRFs) for Protocol CP-2019-001
- ICH Guidance on Statistical Principles for Clinical Trials (E9)
- FDA response to meeting request dated 07 February 2019

Per FDA request, Amendment 3 incorporated changing time zero from the time of the second patch application to be the time of the first patch application, so that the primary efficacy endpoint would be measured at 15 minutes from the start of dosing.

The reader of this SAP is encouraged to also read the clinical protocol, and other identified documents, for details on the planned conduct of this study.

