## 3. OVERALL STUDY DESIGN AND PLAN

This is a phase 2/3, randomized, multicenter, double-blinded, placebo-controlled study that will investigate the efficacy and safety of C213 in the acute treatment of cluster headache attacks. Subjects who have consented and meet the entry criteria will be randomized to receive one of three blinded treatments. Approximately 120 subjects will be randomized. The study is to be conducted at approximately 13 investigational sites in the United States.

Qualified subjects will be randomized to the double-blind treatment period on Day 1 and will have up to 48 weeks to confirm and treat one cluster headache. Using an electronic diary (eDiary) to confirm the subject is experiencing a cluster headache, subjects will self-administer the patches and respond to questions in the eDiary until 1-hour post treatment.

The total duration of this study could be up to approximately 50 weeks over 3 visits, with up to 48 weeks of treatment duration and a variable length of screening (up to 10 days). This study will consist of a Screening visit (Visit 1, up to 1 week prior to randomization), Randomization visit (Visit 2, Day 1), up to a 48-week treatment period (Day 1 - Day 336), and End of Study/Early Discontinuation visit (Visit 3, 1-8 days post-treatment).

Screening activities may be completed over a period as short as one day or spread out over up to one week. At Visit 2, subjects will return to the site for additional baseline assessments and randomization (Day 1). If they meet all study randomization criteria, they will be randomly assigned in a 1:1:1 ratio to receive C213 1.9 mg administered as one active and one placebo patch, C213 3.8 mg administered as two active patches, or placebo administered as two placebo patches.

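### SAP 9.3 groups subjects by entry before or after Amendment 3, which may not match the time zero applied to their treated attack (minor)

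*SAP*

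**What the plan says.** SAP 9.3 (Exploratory Efficacy Analyses) makes its subgroup analysis conditional: "Depending on sample size, the primary efficacy analyses were to be conducted for the subgroup of patients in the mITT population". It then sets the dividing line between the two groups by date of entry, as subjects "who were in the trial prior to Protocol Amendment 3 and for those who were enrolled after Amendment 3". Its aim is stated at the end of the section: "with the purpose of assessing the impact of the modification of time zero to be the start of the first patch application". SAP 1 (Overview) describes the change itself: "Amendment 3 incorporated changing time zero from the time of the second patch application to be the time of the first patch application". The same section gives the protocol and amendment dates: "dated 27 June 2019, Amendment 1, dated 16 July 2019, Amendment 2, dated 01 October 2019 and Amendment 3, dated 15 April 2020".

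Treatment is separated from entry. SAP 3 says that subjects "will have up to 48 weeks to confirm and treat one cluster headache", and a footnote to the schedule in Protocol 6.1 says "Qualifying headache and treatment of a cluster headache must occur within 48 weeks of randomization". The diary is handed over at randomization; Protocol 6.1.2 lists "Provide eDiary training necessary and dispense the eDiary". Protocol Appendix 2 has it activated at that visit.

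Neither document classifies subjects by treatment date, diary version or time zero used. Neither says how the new time zero reached subjects who already held a diary.

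**The concern.** The grouping variable is a proxy for the thing being studied. The question is whether timing from the first or the second patch changes the result. The timing is a property of the treated attack, and SAP 9.3 substitutes the date of entry. With a treatment window of up to 48 weeks, a subject could enter under the old rule, be treated under the new one, and still sit in the earlier-entry subgroup.

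Such subjects would make the earlier-entry subgroup look more like the later one. A real effect of the change would appear smaller than it is, and the check would lean towards finding no difference. This is the only planned analysis that looks at the time-zero change. The primary analysis in SAP 9.1 pools all mITT subjects whichever timing applied.

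**Working it through.** The plan gives no figure for the misclassified share, so the check has four parts.

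**1. Can a subject cross the amendment?**
- Protocol v1.0 is dated 27 June 2019 and Amendment 3 is dated 15 April 2020 (SAP 1): 293 days, or 41.9 weeks.
- The treatment window is 48 weeks, or 336 days (SAP 3; Protocol 6.1).
- For a window to have closed by 15 April 2020, randomization had to fall on or before 15 May 2019, which precedes protocol v1.0.

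So, if the 48-week window applied throughout, every subject still untreated at Amendment 3 could treat after it. A subject randomized on 14 April 2020 could treat as late as 16 March 2021.

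**2. What share (m) of the earlier-entry subgroup could be misplaced?**

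*Case A: dispensed diaries kept second-patch timing.* Entry date then matches the time zero used, and m = 0%.

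*Case B: every diary switched on 15 April 2020.* Assume accrual uniform over the L days before the amendment and all subjects treated within 336 days. Then m is the average of 1 − F(u) for u from 0 to L, where F is the distribution of time to treatment.

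For treatment times uniform over 336 days, m = 1 − L/(2 × 336):
- Accrual from v1.0, L = 293: 1 − 293/672 = 56%.
- Accrual from Amendment 1 (16 July 2019), L = 274: 1 − 274/672 = 59%.

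For exponential times truncated at 336 days, F(u) = (1 − e^(−ru))/(1 − e^(−336r)), with r = ln 2/median (the median before truncation) and L = 293:

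| Median time to treatment | m |
|---|---|
| 7 days | 3% |
| 14 days | 7% |
| 28 days | 14% |
| 56 days | 26% |
| 112 days | 38% |
| 168 days | 44% |

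Case B therefore spans about 3% to 59%.

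**3. Effect on the comparison.** If the misplaced subjects respond as others timed from the first patch do, observed difference between subgroups = true difference × (1 − m). A true 10-point effect would show as:
- m = 3%: 10 × 0.97 = 9.7 points
- m = 25%: 10 × 0.75 = 7.5 points
- m = 50%: 10 × 0.50 = 5.0 points
- m = 59%: 10 × 0.41 = 4.1 points

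Grouping by the time zero actually applied sets m = 0 in both cases.

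**4. How much could the analysis show anyway?** The plan's own power figure (SAP 5: 20% against 55%, 40 per arm, 15% dropout, about 80%) reproduces. With 40 × 0.85 = 34 evaluable per arm and the difference reduced by 1/34 for continuity:

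(0.35 − 0.0294 − 1.96 × 0.1174)/0.1095 = 0.83, giving power of 79.6%.

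The subgroups use Fisher's exact test on fewer subjects. For the same rates, power is about 10% at 5 per arm, 19% at 10 and 34% at 15. These subgroup sizes are illustrative; the documents give none.

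**The case against.** The strongest reply is that misclassification is nowhere shown. The diary is dispensed and activated at randomization. No clinic visit is scheduled between then and the visit after treatment, and no recall or update of issued diaries is described. If those diaries kept second-patch timing, the SAP's split is right as it stands. This reply stands: a reader might infer that the rule in force on the day of treatment set the time zero for everyone, but the documents do not say so.

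It also limits the remedy. Regrouping by treatment date may seem obvious, since Protocol 4.8 has the date and time of dose recorded in the eDiary. But if old diaries kept the old timing, that rule would move correctly placed subjects into the wrong subgroup.

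Three further limits stand:
- The 48-week window comes from the current text; the window in previous protocol versions is not given.
- SAP 9.3 repeats the dose-against-placebo tests within each subgroup and plans no test between subgroups, so any attenuation affects an informal comparison.
- SAP 12 says enrollment fell well short of plan, so failure to see a difference would come mainly from small numbers.

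What the reply does not answer is that the SAP is silent on subjects randomized before but treated after the amendment, and the dates allow such subjects to exist.

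**Conclusion.** The subgroup definition does not match its stated purpose, and the documents leave open whether this matters in practice. The misclassified share is 0% if issued diaries kept the old timing. It is about 3% to 59% if all switched on 15 April 2020, given uniform accrual, treatment of every subject within 336 days and the assumed times to treatment. The documents fix none of these assumptions. A delay in introducing the change at sites could also misplace some later-entry subjects; no delay is given.

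Severity is minor. The analysis is exploratory, conditional on sample size and poorly powered even with perfect grouping. A reader might infer that the primary result is compromised. It is not affected by this point, because SAP 9.1 does not use these subgroups.

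**What to change.** In SAP 9.3, define the two subgroups by the time zero actually applied to each subject's treated attack: timed from the second patch, or timed from the first patch. Determine this from the eDiary version or the eDiary timestamps. Do not use treatment date alone unless it is confirmed that diaries already issued were switched, and when. State how subjects randomized before but treated after Amendment 3 are classified, and report how many there are.

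The cost is about one sentence of SAP text plus a check of the eDiary records. The documents do not show that diary version is held as a data item, so its availability needs confirming. The rule needs no treatment assignments and can be settled before unblinding. If issued diaries were never switched and every later entrant was timed from the first patch, it gives the same groups as the present wording and nothing is lost.

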## 5. SAMPLE SIZE DETERMINATION

The study is planned to enroll approximately 120 subjects total in a 1:1:1 randomization, that is, 40 subjects in each of the placebo, C213 1.9 mg, and C213 3.8 mg groups. It is anticipated that 20% of subjects receiving placebo and 55% of subjects receiving active treatment will achieve pain relief at 15 minutes and sustained pain relief from 15 minutes to 60 minutes post-dose. Based on a two-sided chi-square test with continuity correction and an alpha level of 0.05, 40 subjects per arm will provide approximately 80% power to detect this same difference between two treatment groups, assuming a 15% dropout rate.

Protocol: CP-2019-001 Page 13 of 26

Final Version 1.0

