#### 9. EFFICACY ANALYSES

## 9.1 Primary Efficacy Analysis

The proportion of subjects who achieve pain relief at 15 minutes and the proportion who achieve sustained pain relief from 15 minutes to 60 minutes post patch administration will be analyzed separately using Fisher's Exact test, with missing data imputed using LOCF (see section 7.1.3). The analyses will include all subjects in the mITT population. A significance test of the treatment difference comparing each C213 dose (1.9 mg and 2.8 mg) to placebo will be tested at the two-sided 0.05 level.

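### SAP 9.3 sets out to assess the effect of moving time zero but plans only separate drug-versus-placebo tests in each subgroup, with no comparison between the subgroups

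*SAP*

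**What the plan says.** SAP 9.3 is headed as exploratory and depends on sample size. It plans a repeat of the primary analyses for mITT subjects "who were in the trial prior to Protocol Amendment 3 and for those who were enrolled after Amendment 3". The section also gives its aim. The repeat is done "with the purpose of assessing the impact of the modification of time zero to be the start of the first patch application". SAP 1 explains the change: at the FDA's request, Amendment 3 moved time zero from the second patch to the first, so the clock for both co-primary endpoints starts earlier.

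The analyses to be repeated are defined in SAP 9.1. The two co-primary proportions "will be analyzed separately using Fisher's Exact test". Each dose is compared with placebo, two-sided, at 0.05. SAP 9.1 does not carry over the odds ratios and 95% confidence intervals of protocol 7.4.1. SAP 7.1 does plan frequencies and percentages by treatment group.

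SAP 9.1, 9.2 and 9.3 contain no interaction test and no estimate or interval for a difference between the two subgroups. SAP 12 says that randomization fell well short of plan but does not give the number.

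**The concern.** The question in SAP 9.3 is whether moving time zero changed the result. Its null hypothesis is that the C213-placebo difference is the same in both subgroups. The planned tests have another null: no drug effect within one subgroup. Neither uses data from the other subgroup, so no planned test or interval bears on the stated question, however accurately subjects are classified.

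Two doses, two endpoints and two subgroups give 2 × 2 × 2 = 8 p-values. A reader looking for an impact of time zero is likely to set them side by side. A significant result in one subgroup only may then be read as an impact when the subgroups differ merely by chance or size. Two non-significant results may be read as no impact when both tests were simply too small. This is the only planned analysis of a change to the clock for both co-primary endpoints.

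**Working it through.** **Inputs.** SAP 5 anticipates that "20% of subjects receiving placebo and 55% of subjects receiving active treatment will achieve pain relief at 15 minutes", and the same rates for sustained relief. It plans "approximately 120 subjects total in a 1:1:1 randomization", 40 per arm, with 15% dropout. The test and level are those of SAP 9.1. Subgroup sizes are not given, so they are assumed over a range.

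**The plan's own figure.** Evaluable subjects per arm: 40 × 0.85 = 34. With δ = 0.35, the continuity-corrected effective size has √n* = (34 − 1/0.35)/√34 = 5.341. Then z = (0.35 × 5.341 − 1.96 × √(2 × 0.375 × 0.625)) / √(0.2 × 0.8 + 0.55 × 0.45) = (1.869 − 1.342)/0.638 = 0.826, a power of 79.6%. The stated 80% is reproduced, so these rates are a fair basis.

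**Comparing p-values when time zero has no impact.** Let A and B be the exact power of the two-sided Fisher test at 0.05 in the two subgroups, with 20% against 55% in both.

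- One significant, the other not: A(1 − B) + B(1 − A)
- Both non-significant: (1 − A)(1 − B)

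For 8 per arm in each subgroup: 2 × 0.1737 × 0.8263 = 0.287, and 0.8263² = 0.683.

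| Per arm in each subgroup | Power | One significant, other not | Both non-significant |
|---|---|---|---|
| 4 | 3.8% | 7.2% | 92.6% |
| 5 | 10.5% | 18.8% | 80.2% |
| 6 | 5.4% | 10.2% | 89.5% |
| 7 | 10.8% | 19.3% | 79.5% |
| 8 | 17.4% | 28.7% | 68.3% |
| 10 | 18.6% | 30.3% | 66.3% |
| 17 | 43.6% | 49.2% | 31.8% |
| 20 | 53.2% | 49.8% | 21.9% |

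The values do not rise smoothly because Fisher's test is discrete.

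Unequal splits:

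- 5+15: 0.1047 × 0.6607 + 0.3393 × 0.8953 = 37%
- 10+24: 0.1858 × 0.3671 + 0.6329 × 0.8142 = 58%
- 10+30: 0.1858 × 0.2624 + 0.7376 × 0.8142 = 65%

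The 20+20 and 10+30 rows need all 40 planned subjects per arm in the mITT population; 17+17 and 10+24 need the planned 34.

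If C213 had no effect at all (20% in every arm), discordance would be 0.9% at 8+8 and 4.4% at 20+20.

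**A direct contrast.** The difference between the two risk differences (Agresti-Caffo adjusted), tested at 5% in simulated trials with the same true effect in both subgroups, rejects in 3.3% at 8+8, 3.5% at 10+10 and 4.2% at 20+20. If the effect vanished entirely in one subgroup, it would detect this in only 15%, 20% and 41%. The 95% half-width averages about 51 points at 10+10 and 41 points at 17+17. The unadjusted formula 1.96 × √(2 × (0.16 + 0.2475)/n) gives 56 and 43.

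**The case against.** The analysis is exploratory, optional, and tied to no primary conclusion. SAP 9.3 does not make significance in one subgroup and not the other its criterion; that reading comes from the reader, not the plan. Response proportions by arm would probably be shown in each subgroup under SAP 7.1, so risk differences could be read off. All of this stands and keeps the priority low. What is still missing is any measure of uncertainty for the comparison that SAP 9.3 says it wants to make.

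A reader might take 29-50% as a general rate of false signals. It is not: it needs equal subgroups of 8-20 per arm and a true 35-point effect, and its upper end needs enrolment that SAP 12 says was not reached. Nor should it be judged against 5%. Discordance under a real drug effect is a matter of power, not the type I error of a planned test, and SAP 9.3 sets no decision rule.

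A reader might also infer that a between-subgroup interval would settle the time-zero question. It would not. The subgroups are non-randomised enrolment periods. Amendment 3 also fell in the pandemic and, per SAP 3.4, allowed a remote Visit 3. Subjects have up to 48 weeks to treat, so entry date need not match the clock that applied. And the power shown above is low.

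**Conclusion.** The method in SAP 9.3 does not address its stated purpose: it tests for a drug effect within each subgroup and plans no contrast or interval between them. This follows from the text and needs no assumption about numbers.

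How misleading a comparison of p-values could be depends on sizes that the documents do not give. At the planned rates, for one dose and one endpoint, discordance is about 7-19% at 4-7 per arm per subgroup, where both tests are non-significant in about 80-93% of trials. It is 29-50% at 8-20 per arm in equal subgroups, and up to about 65% for unequal splits such as 10+30. Given the shortfall, the smaller sizes deserve more weight, and there the likelier error is to read two non-significant results as no impact. The documents do not support saying that the plan will produce a false finding at any particular rate. This is a cheap improvement of low priority.

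**What to change.** In SAP 9.3, for each dose and co-primary endpoint, report the C213-placebo risk difference with 95% CI in each subgroup, and the difference between the two risk differences with its 95% CI, in place of relying on separate significance tests. Add two statements:

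- Significance in one subgroup and not the other, or in neither, is not evidence for or against an impact of time zero.
- The contrast is descriptive, because the subgroups are non-randomised enrolment periods that also differ in other ways, such as the pandemic changes.

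The cost is a few lines of SAP text and one table from data already collected, with no extra subjects or procedures. The drawback is that the wide interval will show that little can be concluded about time zero.
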